### 9.2 Unsolicited Adverse Events

(Secondary) Endpoint: All unsolicited AEs reported through 28 days after meningococcal vaccination

Unsolicited Adverse Events (AEs) are anticipated to be collected from the time participants received their assigned meningitis vaccination through 28 days after meningitis vaccination. Per the study protocol, the time of reference for the AE is to be the time from receipt of the randomized blinded meningococcal vaccine. Thus, for participants randomized to receive their meningococcal vaccine at 15-18 months, AEs occurring between Step 1 randomization visit and Step 2 randomization visit are not anticipated to be collected and will not be included as part of safety endpoints.

This safety endpoint includes all unsolicited AEs reported in scheduled or interim (unscheduled) visits after receipt of meningitis vaccination and with date of onset up to and including Study Day 29.

Severity grade for unsolicited AEs is evaluated and reported by site investigators as mild, moderate, severe, potentially life-threatening and death. Unsolicited AEs will be coded by MedDRA for preferred term and corresponding system organ class (SOC). Unsolicited AEs will also be classified as related or not related to study product.

#### Analysis Set: mITT Analysis Set

Approach: The number and percentage of subjects reporting at least one (unsolicited) AE related to study product, overall and for each MedDRA preferred term, will be presented in tables by MedDRA SOC, preferred term, Severity and Study Group. For participants reporting multiple events within the same MedDRA term, the maximum severity grade is counted. Percentages are calculated as the number of participants reporting an event of a specific severity grade divided by the number of participants in the analysis set. Exact 95% CI for the percentage of participants reporting at least one AE, overall and by MedDRA SOC category will be computed.

Graphical display: A bar chart showing unsolicited AEs by MedDRA SOC and severity, as well as a bar chart showing AEs by MedDRA SOC and relationship to study product, will be produced.

Additional Tables/Listings: All Unsolicited AEs will be cross tabulated by severity and relationship to study product, for each Study Group. All adverse events graded as Moderate or above, will be listed. The listing will include Subject ID, MedDRA Preferred Term and AE description verbatim, Severity, Relationship to Study Product, Study Visit where the AE was reported, Onset Date, Time from Vaccination Date to Onset Date, Outcome Date, Duration Days, Action Taken with Study Product, Other Actions, Status/Outcome, if the AE qualifies as SAE, if the AE meet criteria for Suspected Unexpected Serious Adverse reaction (SUSAR), if the event was evaluated for halting criteria and if the AE is a worsening of a baseline medical condition.

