Activities (MedDRA) for preferred term and system organ class SOC. All SAEs will be collected from the time of first vaccination through the end of the study. SAEs will be described by detailed listings showing the event description, MedDRA preferred term and SOC, relevant dates (vaccinations and AEs), severity, relatedness, and outcome for each event. Non-serious unsolicited AEs will be summarized as number and percentage of subjects reporting at least one event in each MedDRA preferred term and SOC, cross tabulated by severity and relationship to study product. Additionally, the proportion of subjects and exact 95% CIs of AEs in aggregate and by MedDRA categories will be computed.

Clinical laboratory data will be summarized as change from baseline and by severity for each visit, and as the maximum over all post study vaccination visits.

Baseline Descriptive Statistics

Summaries of demographic variables such as age at vaccination and sex, will be presented by arm. Summaries of clinical variables, such as weight, length and WHO standardized z-scores of length-for-age, weight-for-age and weight-for-length, at time of vaccination will also be presented by arm.

Tabulation of Individual Subject Data

In general, all data will be listed, sorted by arm and subject, and when appropriate by visit number within subject.

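### SAP 9.2 restricts its only participant-level preferred-term table of unsolicited AEs to related events, so the all-causality table that protocol 9.6 requires is not planned

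*SAP*

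**What the plan says.** SAP 9.2 defines the endpoint without regard to causality: "This safety endpoint includes all unsolicited AEs reported in scheduled or interim (unscheduled) visits after receipt of meningitis vaccination", with onset up to Study Day 29. The main table in its Approach paragraph is narrower: "The number and percentage of subjects reporting at least one (unsolicited) AE related to study product, overall and for each MedDRA preferred term", laid out by SOC, preferred term, severity and Study Group.

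The rest of SAP 9.2 plans all-causality output of other kinds:
- "Exact 95% CI for the percentage of participants reporting at least one AE, overall and by MedDRA SOC category will be computed".
- Bar charts by SOC and severity, and by SOC and relationship.
- "All Unsolicited AEs will be cross tabulated by severity and relationship to study product, for each Study Group".
- A listing of individual events: "All adverse events graded as Moderate or above, will be listed".

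Protocol 9.6 sets this requirement: "Non-serious unsolicited AEs will be summarized as number and percentage of subjects reporting at least one event in each MedDRA preferred term and SOC", and the same sentence continues "cross tabulated by severity and relationship to study product". It also makes a general commitment on listings: "In general, all data will be listed, sorted by arm and subject".

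**The concern.** In the protocol, relationship is a dimension of the preferred-term table, so related and unrelated events both appear. In the SAP it decides which events enter the table. The table is therefore narrower than both the protocol requirement and the SAP's own endpoint.

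Relatedness is an investigator's judgement. Comparing arms on all events, whatever their attribution, guards against a real effect being judged unrelated case by case. If one preferred term occurred more often in one arm but was judged unrelated, the planned tables would show it only pooled with other terms in its SOC. Otherwise someone would have to count it by hand from listings.

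Safety in this trial is descriptive (protocol 9.2), so these tables are the analysis of the endpoint. They feed the two by-age-group reports to WHO (SAP 3.1). Under the same section, an analysis added after the SAP is final is reported as post hoc. That label would not suit a table the protocol already specifies.

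**Working it through.** **1. Does any SAP output supply the missing table?** The requirement is the number and percentage of participants, by preferred term, for all causes.

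| Output in SAP 9.2 or 9.3 | Participant-level | Preferred term | All causes |
|---|---|---|---|
| Main table | yes | yes | no, related only |
| Exact CIs | yes | no, overall and SOC | yes |
| Bar charts | not stated | no, SOC | yes |
| Severity-by-relationship cross-tabulation | not stated | not stated | yes |
| Listing of moderate or worse AEs | no, listing | yes | yes |
| SAE listings (9.3) | no, listing | yes | yes |

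No row meets all three conditions. A mild event judged unrelated and not serious appears by preferred term in no table or listing specified in SAP 9.2 or 9.3. It would appear only under the protocol's general listing commitment.

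**2. Does the SAP override the protocol here?** SAP 3.2 gives the SAP precedence where an analysis set is defined in both documents. It says nothing of the kind for AE summaries, so the two texts conflict.

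**3. How much would the filter remove?** The documents give no figure to reproduce. The Phase 2 trial in Malian children (protocol 1.1.2) gives an illustration. Those children were 12 to 16 months old and the comparator was different.

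Inputs: 375 children randomised 2:2:1; 122 unsolicited AEs after dose 1, of which 2 were judged related, both diarrhoea in the non-adjuvanted NmCV-5 arm, the formulation taken forward; 58 after dose 2, none related; 26%, 25% and 30% of participants with any unsolicited AE after dose 1. This trial plans 400 NmCV-5 infants per age group.

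- Share of events judged related after dose 1: 2/122 = 1.6% (Clopper-Pearson 95% CI 0.2 to 5.8%). The other 120/122 = 98.4% would fall outside a related-only table.
- Size of the non-adjuvanted arm: 375 × 2/5 = 150.
- Children with a related AE: the protocol reports two events, so one or two children.
  - Two: 2/150 = 1.3% (95% CI 0.2 to 4.7%), scaled to 400 × 2/150 = 5.3 infants. The CI limits scale to 0.6 and 18.9, which is not a prediction interval.
  - One: 400 × 1/150 = 2.7 infants.
- Infants with any unsolicited AE: the three percentages carry no arm labels. Taking them in the order the arms are named (control last), the NmCV-5 arms have 25 to 26%, so 400 × 0.25 = 100 to 400 × 0.26 = 104.
- Share of those infants who enter the table:
  - Two children: 5.3/104 = 5.1% to 5.3/100 = 5.3%.
  - One child: 2.7/104 = 2.6% to 2.7/100 = 2.7%.
  - Scaled CI limits for two children: 0.6/104 = 0.6% to 18.9/100 = 18.9%.

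**The case against.** The strongest reply is that the line on cross-tabulating all unsolicited AEs is the protocol's table in shortened form. Its wording nearly repeats the protocol's, where the phrase belongs to the preferred-term and SOC table. On that reading, the SAP plans a related-only table next to the all-causality one. The line does not settle this. It names no preferred term, no SOC and no participant count, while the sentence that does define a preferred-term table states the restriction outright. A programmer could not derive the protocol's table from it.

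Other points stand, in whole or in part:
- The phrase is probably a slip, since the following sentences on maximum severity, percentages and CIs drop the qualifier. That bears on intent, but the instruction remains as written.
- The protocol requirement still applies, so the table could be defended as pre-specified. The SAP's post hoc rule, read literally, would still attach to it.
- The data are not lost. All-causality results by SOC and the listings remain, and the DSMB sees unmasked by-arm reports (SAP 4.1).
- The Phase 2 illustration rests on two events. Even so, at the upper scaled limit about four in five infants with an unsolicited AE would be outside the table.

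**Conclusion.** The concern holds. Followed as written, SAP 9.2 omits a participant-level, all-causality preferred-term table that protocol 9.6 requires. This conclusion comes from comparing the texts and does not depend on the Phase 2 figures.

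If Phase 2 rates carried over, about 3 to 5 of 400 NmCV-5 infants per age group would enter the table, against 100 to 104 with any unsolicited AE. That is roughly 3 to 5% of those infants, or 0.6 to 19% when the CI limits for two children are scaled. It assumes a 150-child Phase 2 arm, one or two children with related events, and the inferred order of the arm percentages.

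The gap is in summarising by preferred term, not in data collection or safety monitoring, and no hypothesis test depends on it. It should be corrected because the endpoint goes into both WHO reports and the correction is minor.

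**What to change.** Delete the words limiting the table to related events from the first sentence of the SAP 9.2 Approach. All unsolicited AEs are then tabulated as number and percentage of participants by SOC, preferred term, maximum severity and vaccine arm within each age group. Show related events as a separate column or a second table.

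To match protocol 9.6 fully, also state that the severity-by-relationship cross-tabulation counts participants within SOC and preferred term. Say whether serious events are included, since the protocol sentence covers non-serious events and SAP 9.3 lists SAEs separately.

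Record the change in the SAP change history before the WHO reports are run, citing protocol 9.6 as its source. The cost is one phrase, a clarifying sentence and an extra column or table. No new data are needed.

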### **9.3 Serious Adverse Events**

Secondary Endpoint: All Serious Adverse Events (SAE), reported during the first 6-months of follow-up period after meningococcal vaccination.

Tertiary Endpoint: All SAEs, reported through 2 years of follow-up or during the entire study period, after meningococcal vaccination.

Unsolicited Adverse events that are reported as Serious Adverse Events (SAEs) according to ICH/GCP or Protocol will be collected from the time of Step 2 randomization and vaccination to through study termination, up to 2 years after meningococcal vaccination. For participants randomized to receive their meningococcal vaccine at 15-17 months, SAEs occurring after Step 1 randomization visit but prior to Step 2 randomization visit may be collected but will not be included in the evaluation of vaccine safety endpoints. Their reporting is described in section 9.4.1.

The secondary endpoint includes all SAEs reported in scheduled or interim (unscheduled) visits after receipt of study meningitis vaccine and with date of onset up to and including Study Day 181.

The tertiary endpoint (to be reported only at the end of the study) includes all SAEs collected in scheduled or interim (unscheduled) visits after receipt of study meningitis vaccine and up to and including the last scheduled Study Visit (Visit 5, scheduled for Study Day 730 ± 45 days).

Analysis Set: mITT Analysis Set

Approach: Serious Adverse Events (SAE), as collected in the Adverse Event eCRF, will be reported in listings, by age and meningococcal vaccination arm. The listing will include Subject ID, MedDRA Preferred Term, AE description verbatim, Severity, Relationship to Study Product, Study Visit where the SAE was reported, Onset Date, time to Onset Date (in days) from study meningitis vaccination, Outcome Date, Duration Days, Action Taken with Study Product, Other Actions, Status/Outcome, Criteria that makes the AE and SAE, if the AE meet criteria for Suspected Unexpected Serious Adverse reaction (SUSAR), if the event was evaluated for halting criteria and if the AE is a worsening of a baseline medical condition.

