9.4.2 Masking Procedures

This section describes blinding of researchers and participants to the random assignment of each individual participant (Step 2 randomization) to receive one of two meningitis vaccines (NmCV-5 or MenACWYTT). Random allocation to receive either meningitis vaccine at 9 months of age or at 15 months of age (Step 1 randomization) will be done open label.

Because the study vaccines may have different appearances, it may not be possible for the vaccinator to be blinded. Designated vaccinators will not partake in any post-vaccination evaluation. Parents or guardians of participants, laboratory personnel, and the researchers responsible for evaluation will remain blinded to participants' random assignment of meningitis study vaccine (Step 2 randomization).

The unblinded designated personnel will be provided with the randomization assignment that includes treatment assignment. Based on the assigned treatment the unblinded personnel will

prepare the study vaccine to be given to each subject. The unblinded personnel will maintain the randomization assignment in a secure location (apart from the rest of the participant file).

Participants and researchers will remain blinded to individual participant random assignment of meningitis study vaccine until after all scheduled activities related to evaluation and collection of specimens are completed at the last study visit (Visit 5, Study Day 730). Unblinding of individual participants' assignment during the conduct of the trial will be generally avoided, but emergency or non-emergency unblinding may be done for safety reasons, as described in the Treatment Unblinding Procedure document. There are no circumstances under which it is expected that unblinding will be necessary for provision of medical treatment or to otherwise protect the safety of study participants. If the site investigator or designee feels that specific product knowledge is necessary to protect participant safety, the site investigator or designee will notify the PC and DMID according to procedures described in the MOP. In the event of a serious adverse event requiring submission to regulatory authorities, unblinding information for the specific participant will be provided by SCHARP as required.

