### **3 GENERAL DATA ANALYSIS CONSIDERATIONS**

#### **3.1 Timing of analyses and reporting**

The main statistical analyses of the primary and secondary immunogenicity endpoints (up to Day 29 visit) and of secondary safety endpoints (up to 6 months of follow-up) will be completed before the end of the study, as soon as the relevant data is available for each of the age groups. Results from these statistical analyses will be summarized in two reports (one per age group), which may be shared with WHO as part of the PQ process.

A first report to be submitted to WHO will include the analysis of primary and secondary endpoints for participants assigned to receive the study vaccine at 9 months of age (Group 1). This report will be produced after the relevant data from all participants in Group 1 through Visit 4 (Study Day 181) has been entered into the study database and appropriate data quality processes have been completed.

A second report to be submitted to WHO will include the analysis of primary and secondary endpoints for all participants assigned to receive the study vaccine at 15 months of age (Group 2). This report will be produced after the relevant data from all participants in Group 2 through Visit 4 (Study Day 181) has been entered into the study database and appropriate processes to ensure data quality have been completed.

The reports described above (which will be referred to as “WHO Reports”) will provide group level results without blinding or masking of the vaccine arms. The analyses will be conducted by the designated unblinded statistician, after the appropriate processes to ensure data quality are completed. The reports can be made available to a limited number of study team members for review, prior to submission to WHO. The list of study members with access to each report should be pre-approved by DMID and IDCRC representatives.

Version 1.0 of this Statistical Analysis Plan (SAP) will be finalized prior to the analyses for the WHO reports being conducted. Any changes or additions to analyses specified here will be properly documented and reported as “post-hoc” when reported.

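### The 6-month SAE endpoint has only a by-arm listing with Subject ID as its output, with no rule keeping it out of the mid-study WHO reports and no arm-level rate

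*SAP*

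**What the plan says.** SAP 9.3 defines two SAE endpoints. The secondary one takes events "with date of onset up to and including Study Day 181". The other is held back: "The tertiary endpoint (to be reported only at the end of the study"). The section sets no such limit on the secondary endpoint. Its only stated output for either endpoint is that events "will be reported in listings, by age and meningococcal vaccination arm. The listing will include Subject ID", along with preferred term, verbatim description, onset date and reporting visit. The analysis set is mITT.

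On timing, SAP 3.1 says the analyses "of secondary safety endpoints (up to 6 months of follow-up) will be completed before the end of the study". For Group 1, "A first report to be submitted to WHO will include the analysis of primary and secondary endpoints", and a second report does the same for Group 2. These reports "will provide group level results without blinding or masking of the vaccine arms". On access, "The reports can be made available to a limited number of study team members for review, prior to submission to WHO"; DMID and IDCRC representatives approve the readers beforehand, and a designated unblinded statistician runs the analyses.

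On the blind, Protocol 9.4.2 says "Participants and researchers will remain blinded to individual participant random assignment of meningitis study vaccine until after all scheduled activities" are finished at Visit 5 (Day 730). SAP 2.5 repeats this. Protocol 9.6 describes the mid-study unblinded results as coming from grouped analysis.

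**The concern.** A listing that shows arm against Subject ID is individual-level unblinding for anyone who reads it. SAE collection and the study physician's relatedness judgement continue to Visit 5, well after Day 181. A reader who also assesses participants would know the arm of particular infants while those judgements were still being made.

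The second issue is what the WHO reports can say about serious events. Allocation is 2:1, so under equal risk the NmCV-5 listing is expected to hold twice as many infants as the control listing. Without a planned percentage by arm, the reader has to correct for that alone. Protocol 7.2 includes SAEs among the events to be assessed by frequency and severity, and SAP 9.3 plans no frequency.

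**Working it through.** The plan states no SAE rate or precision, so there is no figure to reproduce. The check is mainly textual, with short arithmetic for size.

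**Does the endpoint belong in the WHO reports?** SAP 3.1 puts secondary endpoints, including safety to 6 months, in both reports. SAP 9.3 labels SAEs to Day 181 as secondary. So the endpoint belongs there.

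**Is the listing held back?** SAP 7.4 to 7.6 confine baseline medical history, physical examination and medication outputs to end-of-study reports. SAP 9.4.1 assigns the pre-vaccination SAE listing to the final study report. SAP 9.3 restricts only the tertiary endpoint.

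**Two readings:**
- *SAP 9.3 governs.* The identified by-arm listing enters a report that team members may read. This conflicts with SAP 2.5, Protocol 9.4.2 and the group-level wording of SAP 3.1.
- *The group-level wording governs.* The listing stays out, and the 6-month SAE endpoint has no specified output in the report.

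**Is an SAE rate planned elsewhere?** The SAP 9.2 tables stop at onset on Day 29 and do not separate serious events. Protocol 9.6 plans proportions for AEs in aggregate, and plans SAEs as listings. Neither gives an SAE-specific rate, and nothing in SAP 9.2 covers Day 30 to Day 181.

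**How long before the blind would end?** On scheduled days, 730 − 181 = 549 days, and 549 / 30.44 ≈ 18 months. This is an upper limit, because each report waits for Visit 4 data from the whole group and for data cleaning. The documents do not give the accrual period. Taking the protocol summary's approximate figures at face value, 48 months for the study less 30 months for the longest participation leaves about 18 months of accrual. The first infant in a group would then be about 18 + 6 = 24 months past vaccination when the last reaches Visit 4, so remaining follow-up would run from about 0 to 18 months.

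**How many infants?** Inputs: 400 and 200 infants per age group (SAP Table 1) and an assumed SAE risk r by Day 181, equal in both arms. Expected number listed = 600r. Chance of at least one = 1 − (1 − r)^600. The exact interval for x of n, the SAP section 5 method, runs from the 2.5% point of Beta(x, n − x + 1) to the 97.5% point of Beta(x + 1, n − x).

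| Assumed r | Infants listed | P(at least one) | NmCV-5, % (95% CI) | MenACWY-TT, % (95% CI) |
|---|---|---|---|---|
| 0.5% | 3 | 95.1% | 2/400: 0.5 (0.06 to 1.79) | 1/200: 0.5 (0.01 to 2.75) |
| 1% | 6 | 99.8% | 4/400: 1.0 (0.27 to 2.54) | 2/200: 1.0 (0.12 to 3.57) |
| 2% | 12 | >99.9% | 8/400: 2.0 (0.87 to 3.90) | 4/200: 2.0 (0.55 to 5.04) |
| 5% | 30 | >99.9% | 20/400: 5.0 (3.08 to 7.62) | 10/200: 5.0 (2.42 to 9.00) |

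With no events, the intervals would be 0 to 0.92% and 0 to 1.83%. The last two columns show what the missing table would report.

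**The case against.** The strongest reply is that no sentence sends the SAP 9.3 listing to WHO. SAP 2.1 says only selected analyses go into those reports, and both documents describe their results as grouped. Readers are few and pre-approved, and nothing says they assess participants. By the time a report exists, the Day 29 serology and the 7-day, 28-day and 6-month safety windows have closed for that group. Protocol 9.4.2 also permits some individual unblinding, for safety reasons or regulatory submission of a serious event. Listing SAEs individually matches Protocol 9.6. Denominators exist, since the mITT set is named and SAP 6.2.1 reports numbers vaccinated by arm.

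Most of this stands, and it rules out three inferences a reader might draw:
- *That the plan will unblind infants to the study team.* This happens only if the listing is included as written. Bias in causality judgements further requires an approved reader who also evaluates participants, which the documents neither state nor exclude.
- *That every listed infant is unblinded 18 months early.* That figure is the maximum.
- *That comparable rates cannot be obtained.* A reader could derive them from the listing and the arm sizes; they are simply not prespecified.

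The reply does not remove the gap. The exceptions in Protocol 9.4.2 are case by case and do not cover a listing of every SAE. If the grouped wording excludes the listing, nothing is specified in its place.

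**Conclusion.** The point holds as a conditional conflict plus an omission. The conflict depends on the SAP 9.3 listing being placed in a WHO report; if it is, it affects only infants with an SAE by Day 181, only the approved readers, and at most about 18 months of remaining follow-up. At assumed risks of 0.5% to 5%, that means 3 to 30 infants listed per age group, some of them at or near Visit 5 by then. The omission depends on neither reading: no SAE-specific arm-level count, percentage or interval is planned for the 6-month endpoint. No primary result is affected. The change is worth making because it protects the blind and gives WHO rates that can be compared under 2:1 allocation.

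**What to change.** In SAP 9.3, add a table on the mITT set giving the number, percentage and exact (Clopper-Pearson) 95% CI of infants with at least one SAE, and with at least one related SAE, by arm and age group. Name it as the SAE output for the WHO reports.

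State that any SAE listing study team members can read before all Visit 5 activities are complete omits arm. Removing Subject ID alone is not enough, because verbatim description, onset date and visit could let site staff recognise an infant. Reserve identified by-arm listings for the DSMB closed report and the final report, and cross-refer to SAP 2.5 and 3.1 so the three sections agree.

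The cost is revised SAP wording and one small table. No new data are needed.
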